7.1.4.4 Calibration of Critical Equipment

The investigator or qualified designee has the responsibility to ensure that any critical device or instrument used for a clinical evaluation/test during a clinical trial that provides important information about inclusion/exclusion criteria and/or safety or efficacy parameters shall be suitably calibrated and maintained to ensure that the data obtained is reliable and/or

reproducible. Documentation of equipment calibration must be retained as source documentation at the trial site.

Critical Equipment for this trial includes:

- Laboratory equipment - as required for inclusion labs and trial assessments
- Imaging equipment - as required for trial objectives
- Infusion equipment - as required for administering drug product.

See protocol-specified guidance in the Administrative Binder, Procedures Manual, Pharmacy Manual, and Site Imaging Manual.

7.1.5 Visit Requirements

Visit requirements are outlined in Section 6.0 - Trial Flow Chart. Specific procedure-related details are provided above in Section 7.1 - Trial Procedures.

7.1.5.1 Screening

Approximately 28 days prior to treatment allocation/randomization, potential subjects will be evaluated to determine that they fulfill the entry requirements as set forth in Section 5.1. Screening procedures may be repeated after consultation with the Sponsor.

Written consent for the main trial must be obtained prior to performing any protocol-specific procedure. Results of a test performed prior to the subject signing consent as part of routine clinical management are acceptable in lieu of a screening test if performed within the specified time frame. Screening procedures are to be completed within 28 days prior to the first dose of trial treatment except for the following:

- For women of reproductive potential, a urine pregnancy test will be performed within 72 hours prior to the first dose of trial treatment. If urine pregnancy results cannot be confirmed as negative, a serum pregnancy test will be required (performed by the local trial site laboratory).

Subjects may be rescreened 1 time after initially failing to meet the inclusion/exclusion criteria. Results from assessments performed during the initial screening period are acceptable in lieu of a repeat screening test if performed within the specified time frame and the inclusion/exclusion criteria is met.

7.1.5.2 Treatment Period

Visit requirements are outlined in Section 6– Trial Flow Chart. Specific procedure-related details are provided above in Section 7.1 – Trial Procedures.

7.1.5.3 Post-Treatment Visits

Antineoplastic treatments started after trial treatment completion are collected during Follow-up and Survival Follow-up.

7.1.5.3.1 Safety Follow-Up Visit

The mandatory Safety Follow-Up Visit should be conducted approximately 30 days after the last dose of trial treatment **or before the initiation of a new antineoplastic treatment, whichever comes first**. All AEs that occur prior to the Safety Follow-Up Visit should be recorded. Subjects with an AE of Grade > 1 will be followed until the resolution of the AE to Grade 0-1 or until the beginning of a new antineoplastic therapy, whichever occurs first. SAEs that occur within 90 days of the end of treatment or before initiation of a new antineoplastic treatment should also be followed and recorded.

7.1.5.4 Efficacy Follow-up Visits

Subjects who complete the protocol-required cycles of treatment or who discontinue trial treatment for a reason other than confirmed PD will move into the Follow-Up Phase and should be assessed every 12 weeks (\pm 14 days) for at least 12 months to monitor disease status (Section 6). Every effort should be made to collect information regarding disease response status until the start of new antineoplastic therapy, documented PD by investigator assessment, death, or end of the trial. Information regarding post-trial antineoplastic treatment will be collected if new treatment is initiated.

7.1.5.4.1 Follow-Up Post-Allogeneic Stem Cell Transplantation

For subjects who have an allogeneic SCT within 24 months of last dose of pembrolizumab or before the end of the trial, transplant parameters will be collected, and specific events will be collected as ECIs for 18 months from the date of the allogeneic transplant or until the end of the trial, to include graft-versus-host-disease, hepatic veno-occlusive disease and/or sinusoidal syndrome, febrile syndrome (a steroid-requiring febrile illness without an infectious cause), pulmonary complications, immune-mediated AEs, critical illness, and transplant-related mortality, for all grades, and regardless of relationship to trial drug. Additional medically important AEs post-allogeneic SCT may be submitted at the investigator's discretion (Section 7.2.3.2.1). If available and relevant to an event post-allogeneic SCT, concomitant medications and/or laboratory results may also be reported.

Post-allogenic-SCT ECIs that occur after the normal safety follow-up period must be assessed for seriousness and causality and reported to the sponsor as follows: within 24 hours if serious regardless of causality or if non-serious and considered to be drug related; and 5 calendar days if non-serious and not considered to be drug related.

Guidance on details to be collected and suggested events to be reported can be found in the Procedure Manual.

7.1.5.4.2 Survival Follow-up

Once a subject experiences confirmed disease progression or starts a new antineoplastic therapy, the subject moves into the survival follow-up phase and should be contacted by telephone every 12 weeks (\pm 14 days) to assess for survival status until death, withdrawal of consent, or the end of the trial, whichever occurs first. The first survival follow-up assessment should be scheduled as described below:

For participants who discontinue treatment intervention and who will not enter the efficacy follow-up phase, the first survival follow-up assessment will be scheduled 12 weeks after the discontinuation visit and/or safety follow-up visit (whichever is last).

For participants who completed assessments in the efficacy follow-up phase, the first survival follow-up assessment will be scheduled 12 weeks after the last efficacy assessment follow-up visit has been performed.

7.1.5.4.3 Survival Status

To ensure current and complete survival data are available at the time of database locks, updated survival status may be requested during the course of the trial by the Sponsor. For example, updated survival status may be requested prior to but not limited to an external Data Monitoring Committee review, interim and/or final analysis. Upon Sponsor notification, all participants who do not/will not have a scheduled trial visit or trial contact during the Sponsor-defined time period will be contacted for their survival status (excluding participants that have a previously recorded death event in the collection tool).

7.2 Assessing and Recording Adverse Events

An adverse event is defined as any untoward medical occurrence in a patient or clinical investigation subject administered a pharmaceutical product and which does not necessarily have to have a causal relationship with this treatment. An adverse event can therefore be any unfavourable and unintended sign (including an abnormal laboratory finding, for example), symptom, or disease temporally associated with the use of a medicinal product or protocol-specified procedure, whether or not considered related to the medicinal product or protocol-specified procedure. Any worsening (i.e., any clinically significant adverse change in frequency and/or intensity) of a preexisting condition that is temporally associated with the use of the Sponsor's product, is also an adverse event.

Changes resulting from normal growth and development that do not vary significantly in frequency or severity from expected levels are not to be considered adverse events. Examples of this may include, but are not limited to, teething, typical crying in infants and children and onset of menses or menopause occurring at a physiologically appropriate time.

Sponsor's product includes any pharmaceutical product, biological product, device, diagnostic agent or protocol-specified procedure, whether investigational (including placebo or active comparator medication) or marketed, manufactured by, licensed by, provided by or distributed by the Sponsor for human use.

Adverse events may occur during clinical trials, or as prescribed in clinical practice, from overdose (whether accidental or intentional), from abuse and from withdrawal.

All adverse events that occur after the consent form is signed but before treatment allocation/randomization must be reported by the investigator if they cause the subject to be excluded from the trial, or are the result of a protocol-specified intervention, including but not limited to washout or discontinuation of usual therapy, diet, placebo treatment or a procedure. From the time of treatment allocation/randomization through 30 days following cessation of treatment, all adverse events must be reported by the investigator. Such events will be recorded at each examination on the Adverse Event case report forms/worksheets. The reporting timeframe for adverse events meeting any serious criteria is described in

section 7.2.3.1. The investigator will make every attempt to follow all subjects with non-serious adverse events for outcome.

Electronic reporting procedures can be found in the EDC data entry guidelines. Paper reporting procedures can be found in the Investigator Trial File Binder (or equivalent).

Adverse events will not be collected for subjects during the pre-screening period (for determination of archival tissue status) as long as that subject has not undergone any protocol-specified procedure or intervention. If the subject requires a blood draw, fresh tumor biopsy etc., the subject is first required to provide consent to the main study and AEs will be captured according to guidelines for standard AE reporting.

7.2.1 Definition of an Overdose for This Protocol and Reporting of Overdose to the Sponsor

For purposes of this trial, an overdose will be defined as any dose exceeding the prescribed dose for pembrolizumab defined as any dose of ≥ 1000 mg (5 times the protocol-defined dose), and for dinaciclib defined as any dose > 70 mg/m². No specific information is available on the treatment of overdose of pembrolizumab or dinaciclib. In the event of overdose, pembrolizumab or dinaciclib should be discontinued and the subject should be observed closely for signs of toxicity. Appropriate supportive treatment should be provided if clinically indicated.

If an adverse event(s) is associated with (“results from”) the overdose of Sponsor's product or vaccine, the adverse event(s) is reported as a serious adverse event, even if no other seriousness criteria are met.

If a dose of Sponsor's product or vaccine meeting the protocol definition of overdose is taken without any associated clinical symptoms or abnormal laboratory results, the overdose is reported as a non-serious Event of Clinical Interest (ECI), using the terminology “accidental or intentional overdose without adverse effect.”

All reports of overdose with and without an adverse event must be reported by the investigator within 24 hours to the Sponsor either by electronic media or paper. Electronic reporting procedures can be found in the EDC data entry guidelines. Paper reporting procedures can be found in the Investigator Trial File Binder (or equivalent).

7.2.2 Reporting of Pregnancy and Lactation to the Sponsor

Although pregnancy and lactation are not considered adverse events, it is the responsibility of investigators or their designees to report any pregnancy or lactation in a subject (spontaneously reported to them) that occurs during the trial.

Pregnancies and lactations that occur after the consent form is signed but before treatment allocation/randomization must be reported by the investigator if they cause the subject to be excluded from the trial, or are the result of a protocol-specified intervention, including but not limited to washout or discontinuation of usual therapy, diet, placebo treatment or a procedure. Pregnancies and lactations that occur from the time of treatment allocation/randomization through 120 days following cessation of Sponsor's product, or 30 days following cessation of treatment if the subject initiates new anticancer therapy, whichever is earlier, must be reported by the investigator. All reported pregnancies must be

followed to the completion/termination of the pregnancy. Pregnancy outcomes of spontaneous abortion, missed abortion, benign hydatidiform mole, blighted ovum, fetal death, intrauterine death, miscarriage and stillbirth must be reported as serious events (Important Medical Events). If the pregnancy continues to term, the outcome (health of infant) must also be reported.

Such events must be reported within 24 hours to the Sponsor either by electronic media or paper. Electronic reporting procedures can be found in the EDC data entry guidelines. Paper reporting procedures can be found in the Investigator Trial File Binder (or equivalent).

Although pregnancy and lactation are not considered adverse events, it is the responsibility of investigators or their designees to report any pregnancy or lactation in a subject (spontaneously reported to them), including the pregnancy of a male subject's female partner that occurs during the trial.

Pregnancies and lactations of subjects and female partners of male subjects from the time the consent form is signed but before treatment allocation/randomization must be reported by the investigator if they cause the subject to be excluded from the trial, or are the result of a protocol-specified intervention, including but not limited to washout or discontinuation of usual therapy, diet, placebo treatment or a procedure. Pregnancies and lactations of subjects and female partners of male subjects that occur from the time of treatment allocation/randomization through 14 days following cessation of Sponsor's product must be reported. All reported pregnancies must be followed to the completion/termination of the pregnancy. Pregnancy outcomes of spontaneous abortion, missed abortion, benign hydatidiform mole, blighted ovum, fetal death, intrauterine death, miscarriage and stillbirth must be reported as serious events (Important Medical Events). If the pregnancy continues to term, the outcome (health of infant) must also be reported.

Such events must be reported within 24 hours to the Sponsor either by electronic media or paper. Electronic reporting procedures can be found in the EDC data entry guidelines. Paper reporting procedures can be found in the Investigator Trial File Binder (or equivalent).

7.2.3 Immediate Reporting of Adverse Events to the Sponsor

7.2.3.1 Serious Adverse Events

A serious adverse event is any adverse event occurring at any dose or during any use of Sponsor's product that:

- Results in death;
- Is life threatening;
- Results in persistent or significant disability/incapacity;
- Results in or prolongs an existing inpatient hospitalization;
- Is a congenital anomaly/birth defect;
- Is an other important medical event.

Note: In addition to the above criteria, adverse events meeting either of the below criteria, although not serious per ICH definition, are reportable to the Sponsor in the same timeframe

as SAEs to meet certain local requirements. Therefore, these events are considered serious by the Sponsor for collection purposes.

- Is a new cancer (that is not a condition of the study);
- Is associated with an overdose.

Refer to [Table 17](#) for additional details regarding each of the above criteria.

For the time period beginning when the consent form is signed until treatment allocation/randomization, any serious adverse event, or follow up to a serious adverse event, including death due to any cause, other than progression of the cancer under study (reference Section 7.2.3.3 for additional details), that occurs to any subject must be reported within 24 hours to the Sponsor if it causes the subject to be excluded from the trial, or is the result of a protocol-specified intervention, including but not limited to washout or discontinuation of usual therapy, diet, placebo treatment or a procedure.

For the time period beginning at treatment allocation/randomization through 90 days following cessation of treatment, or 30 days following cessation of treatment if the subject initiates new anticancer therapy, whichever is earlier, any serious adverse event, or follow up to a serious adverse event, including death due to any cause, other than progression of the cancer under study (reference Section 7.2.3.3 for additional details), whether or not related to the Sponsor's product, must be reported within 24 hours to the Sponsor either by electronic media or paper. Electronic reporting procedures can be found in the EDC data entry guidelines. Paper reporting procedures can be found in the Investigator Trial File Binder (or equivalent).

Additionally, any serious adverse event, considered by an investigator who is a qualified physician to be related to the Sponsor's product that is brought to the attention of the investigator at any time following consent through the end of the specified safety follow-up period specified in the paragraph above, or at any time outside of the time period specified in the previous paragraph also must be reported immediately to the Sponsor.

All subjects with serious adverse events must be followed up for outcome.

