5.2.1.2.1 Pembrolizumab Dose Modification

Dose Modification and Toxicity Management for Immune-Related Adverse Events Associated with Pembrolizumab

Adverse events associated with pembrolizumab exposure may represent an immunologic etiology. These immune-related AEs (irAEs) may occur shortly after the first dose or several months after the last dose of pembrolizumab treatment and may affect more than one body system simultaneously. Therefore, early recognition and initiation of treatment is critical to reduce complications. Based on existing clinical trial data, most irAEs were reversible and could be managed with interruptions of pembrolizumab, administration of corticosteroids and/or other supportive care. For suspected irAEs, ensure adequate evaluation to confirm etiology or exclude other causes. Additional procedures or tests such as bronchoscopy, endoscopy, skin biopsy may be included as part of the evaluation. Based on the severity of irAEs, withhold or permanently discontinue pembrolizumab and administer corticosteroids. Dose modification and toxicity management guidelines for irAEs associated with pembrolizumab are provided in [Table 4](#).

Table 4 Dose Modification and Toxicity Management Guidelines for Immune-Related Adverse Events Associated with Pembrolizumab

General instructions:	

 1. Corticosteroid taper should be initiated upon AE improving to Grade 1 or less and continue to taper over at least 4 weeks. 2. For situations where pembrolizumab has been withheld, pembrolizumab can be resumed after AE has been reduced to Grade 1 or 0 and corticosteroid has been tapered. Pembrolizumab should be permanently discontinued if AE does not resolve within 12 weeks of last dose or corticosteroids cannot be reduced to ≤ 10 mg prednisone or equivalent per day within 12 weeks. 3. For severe and life-threatening irAEs, IV corticosteroid should be initiated first followed by oral steroid. Other immunosuppressive treatment should be initiated if irAEs cannot be controlled by corticosteroids. 	

Immune-Related AEs	Toxicity Grade or Conditions (CTCAEv4.0)	Action Taken to Pembrolizumab	irAE Management with Corticosteroid and/or Other Therapies	Monitor and Follow-up

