6.0 TRIAL FLOW CHART

Trial Period:	Screening Phase	Treatment Cycles (21-day cycles) To Be Repeated Beyond 3 Cycles							End of Treatment		Post-Treatment	
Treatment Cycle (21 Day cycles)	Screening ^b	Cycle 1		Cycle 2		Cycle 3 +		Every 3 Cycles (ie, Cycle 4, 7, 10, etc)	Discon	Post-Treatment Safety Follow-up	Efficacy Follow-up Visits	Survival Follow-up
Cycle Day ^a (± 3 days unless otherwise specified)	-28 to -1	1	8	1	8	1	8	1 (± 7 d)	At time of Discon	30 days post Discon ^v	Every 12 weeks post Discon (± 14 d)	Every 12 weeks (± 14 d)
Administrative Procedures												
Informed Consent ^c	X											
Informed Consent for Future Biomedical Research ^d	X											
Inclusion/Exclusion Criteria	X											
Subject Identification Card	X											
Demographics and Medical History	X											
Prior Treatment Review	X											
Concomitant Medication Review ^e	X	X	X	X	X	X	X		X	X		
Post-trial Anticancer Therapy Status ^f										X	X	
Survival ^g		←----->										X
Pembrolizumab Administration		X		X		X						
Dinaciclib Administration		X	X	X	X	X	X					
Clinical Procedures/Assessments												
Full Physical Examination	X	X	X	X		X			X		X	
12-Lead Electrocardiogram	X											
Height ^h	X											
Vital Signs and Weight ^h	X	X	X	X	X	X	X		X		X	
ECOG Performance Status	X	X		X		X			X		X	
Adverse Event Review	X	X	X	X	X	X	X		X	X		
CLL : CT of Neck, Chest, Abdomen, and Pelvis	X							X	X		X	
CLL : Disease Response Assessment	X							X	X		X	
CLL : Constitutional Symptoms	X							X	X		X	
MM : Disease Response Assessment ⁱ	X			X		X			X		X	
MM : Skeletal Survey ^j	X							PRN				
MM : MRI or CT/PET for Extramedullary Soft Tissue Plasmacytoma ^j	X							PRN				

Trial Period:	Screening Phase	Treatment Cycles (21-day cycles) To Be Repeated Beyond 3 Cycles							End of Treatment		Post-Treatment	
		Cycle 1		Cycle 2		Cycle 3 +		Every 3 Cycles (ie, Cycle 4, 7, 10, etc)	Discon	Post-Treatment Safety Follow-up	Efficacy Follow-up Visits	Survival Follow-up
Treatment Cycle (21 Day cycles)	Screening ^b	Cycle 1		Cycle 2		Cycle 3 +		Every 3 Cycles (ie, Cycle 4, 7, 10, etc)	Discon	Post-Treatment Safety Follow-up	Efficacy Follow-up Visits	Survival Follow-up
Cycle Day ^a (± 3 days unless otherwise specified)	-28 to -1	1	8	1	8	1	8	1 (± 7 d)	At time of Discon	30 days post Discon ^v	Every 12 weeks post Discon (± 14 d)	Every 12 weeks (± 14 d)
DLBCL: PET/CT Neck, Chest, Abdomen, and Pelvis ^k	X							X	X		X	
DLBCL: Lymphoma B Symptoms	X							X	X		X	

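### No adverse-event review is scheduled after the 30-day safety visit although the SAE window runs to day 90, and two sections close that window differently when new therapy starts, so SAEs in days 31 to 90 may be under-ascertained.

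*Combined protocol and SAP*

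**What the plan says.** - **Reporting rule.** Section 7.2.3.1 requires all SAEs, whatever their relation to treatment, to reach the sponsor within 24 hours. The period runs from allocation "through 90 days following cessation of treatment, or 30 days following cessation of treatment if the subject initiates new anticancer therapy, whichever is earlier". The closing sentence of Section 7.2's paragraph on reporting periods points to Section 7.2.3.1 for the SAE timeframe.
- **Safety follow-up rule.** Section 7.1.5.3.1 says that "SAEs that occur within 90 days of the end of treatment or before initiation of a new antineoplastic treatment should also be followed and recorded".
- **All adverse events.** Section 7.2 sets a shorter period: "through 30 days following cessation of treatment, all adverse events must be reported by the investigator".
- **Schedule.** In the flow chart (Section 6.0) the "Adverse Event Review" row is marked at screening, at each Day 1 and Day 8 visit, at discontinuation and at the 30-day safety visit. It is blank under Efficacy Follow-up and Survival Follow-up. The blood count and chemistry rows also end at the safety visit.
- **Next contact.** Under Section 7.1.5.4.2, a subject who does not enter efficacy follow-up has a first survival call 12 weeks after the later of the discontinuation and safety visits. Efficacy visits are every 12 weeks after discontinuation. Both carry a 14-day tolerance.
- **Late toxicity.** Section 5.2.1.2.1 says that immune-related events "may occur shortly after the first dose or several months after the last dose of pembrolizumab treatment".
- **Open-ended clause.** The end of Section 7.2.3.1 keeps any SAE judged related reportable without time limit once the investigator learns of it.

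**The concern.** Safety and tolerability are the primary objective in both phases (Section 3.1), and there is no control group. Collecting every SAE regardless of attribution protects the safety summary from depending on a causality judgment. That judgment is hard to make in relapsed disease, and harder once another therapy has begun. The 90-day window states this intention, but the visit schedule does not carry it out: after day 30 no scheduled contact includes a question about adverse events.

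The two closing rules add a second problem. Sites that follow different sections may record different events. Section 8 does not settle which are tabulated, because Section 8.4.2 only refers back to Section 7.2.

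**Working it through.** The plan states no figure to reproduce here. The check is a calendar and a comparison of the two rules.

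**1. Calendar**

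Inputs: safety visit about 30 days after the last dose (Section 7.1.5.3.1); 12 weeks = 84 days, ±14 (Section 6.0, Sections 7.1.5.4 and 7.1.5.4.2); SAE window to day 90 (Section 7.2.3.1).

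- Part of the window after the last scheduled AE review: 90 − 30 = 60 days.
- First survival call after a day-30 safety visit: 30 + 84 = day 114, range 114 − 14 = 100 to 114 + 14 = 128. Even the earliest call is after day 90, so these subjects have no scheduled contact in days 31 to 90.
- First efficacy visit: day 84, range 70 to 98, counted from discontinuation rather than from the last dose. It includes a physical examination, vital signs, ECOG status and disease assessment, but no AE review.

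**2. Closing rules when new therapy starts on day S**

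The word joining the two conditions in Section 7.1.5.3.1 can be read in two ways: the window ends at whichever condition comes first, or meeting either condition is enough.

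| S | 7.2.3.1 ends | 7.1.5.3.1 ends, first to occur | 7.1.5.3.1 ends, either suffices |
|---|---|---|---|
| 10 | 30 | 10 | 90 |
| 45 | 30 | 45 | 90 |
| 60 | 30 | 60 | 90 |
| 85 | 30 | 85 | 90 |

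For S after day 30 and before day 90, both readings of Section 7.1.5.3.1 end later than Section 7.2.3.1, by at least S − 30 days: 15, 30 and 55 days in the last three rows, and 59 at S = 89. For S = 10 the two readings fall on opposite sides of day 30, so neither the direction nor the size of the difference is established.

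**3. Which events are affected**

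Take an SAE on day 45 and new therapy on day 60.

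- Known to the site on day 45: no new therapy has started, the limit is still day 90, and the report is due within 24 hours. Nothing is lost.
- First learned of at the survival call and judged unrelated: outside the window under Section 7.2.3.1 (45 > 30), inside it under Section 7.1.5.3.1 (45 < 60).
- Judged related: reportable whenever it is learned of.

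**4. Illustration only**

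The documents give neither a rate of SAEs in days 31 to 90 nor a capture rate. Assume a rate p of 5% or 10% and a capture proportion c between 50% and 100%, in a cohort of 30 (Section 8.8). Expected cases captured are 30pc, and the probability of seeing at least one is 1 − (1 − pc)^30.

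- p = 5%: captured cases fall from 1.5 (c = 100%) to 0.75 (c = 50%), and the probability from 0.785 to 0.532.
- p = 10%: captured cases fall from 3.0 to 1.5, and the probability from 0.958 to 0.785.

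This shows how capture matters in a small cohort. It does not estimate the loss in this trial.

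**The case against.** A reader might infer that late immune SAEs will be under-counted. The documents do not support that. An SAE recognised as immune-related to pembrolizumab is a related SAE, and Section 7.2.3.1 keeps it reportable at any time. No size of loss can be calculated.

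A reader might also infer that nothing is collected after day 30. That is too broad:

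- Section 7.1.2.6 says AEs are recorded during follow-up, and assessed more often than scheduled if clinically indicated.
- Section 7.1.2.2 makes new significant examination findings AEs, and efficacy visits include an examination.
- Section 7.1.5.3.1 follows AEs above Grade 1 until they improve or new therapy begins.
- Section 7.1.5.4.1 collects specified events after allogeneic transplant.
- Survival calls identify deaths.

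On the closing rules, Section 7.2 names Section 7.2.3.1 as the place for the SAE timeframe, and an SAE already known on day 45 is not un-reported by therapy starting on day 60. The consequence is also limited: the stated primary endpoint is DLT, observed in Cycles 1 and 2, and all rrMM and rrCLL subjects are off treatment.

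These points narrow the concern but do not remove it. The open-ended clause needs both a judgment of relatedness and knowledge of the event, and it creates no contact. Section 7.1.2.6 takes its visit timing from the flow chart, which is blank after day 30. A hospitalisation on day 45 that has resolved may leave nothing to find on examination near day 84, and subjects followed only by telephone have no examination. Naming one section as controlling does not bring the other into line with it.

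**Conclusion.** Two points stand. First, the plan requires all SAEs through day 90 but schedules no AE review after day 30. Subjects outside efficacy follow-up have no scheduled contact until about day 114 (100 to 128), assuming a day-30 safety visit. SAEs in days 31 to 90 may be under-ascertained, mainly those judged unrelated or unknown to the investigator. The 60-day interval measures the gap in the schedule, not the share of events missed.

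Second, Sections 7.1.5.3.1 and 7.2.3.1 conflict for new therapy started between days 30 and 90, by at least S − 30 days when Section 7.2.3.1 is read literally. This mainly affects unrelated-judged SAEs learned of late, and which events are tabulated. It is tempting to add that the order of the two rules reverses for therapy started before day 30. That follows from only one reading of Section 7.1.5.3.1, so the text there is ambiguous rather than shown to conflict in a given direction.

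The correction is worth making because it is inexpensive and serves the primary objective. Its practical reach is mainly the remaining DLBCL subjects.

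**What to change.** - **One closing rule in both sections.** With Section 7.2.3.1 as the controlling text, bring Section 7.1.5.3.1 into line, using a rule that cannot close the window retroactively. For example: all SAEs through day 90 after the last dose or, if new anticancer therapy starts earlier, through the later of day 30 and the start date of that therapy.
- **Flow chart.** Mark an SAE question covering events through day 90 at the first efficacy follow-up visit and the first survival call. Where that contact falls before day 90, as an efficacy visit between days 70 and 89 would, complete the question at the next contact.
- **Section 8.4.2.** State that SAEs are tabulated over the same window.

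The cost is protocol wording, two flow-chart marks and a short question at contacts that already take place. The downside is slightly more SAE reports, some of them reflecting the disease rather than treatment.
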